Target number of participants	We anticipate to recruit 800 participants for this study over the course of 4 years

Criteria for evaluation	
Primary outcome measure(s): The primary outcome of the study is to evaluate if specific heritable arrhythmic disorders are associated with changes in selected protein distribution/expression levels at cell-cell junctions within the buccal mucosa. Our preliminary studies suggest that protein distribution/expression alterations in the buccal mucosa mirror equivalent changes that occur in the myocardium of patients with ACM. This study will evaluate the use of this "novel diagnostic tool" in individuals at risk of sudden cardiac death due to other, more common forms of arrhythmic disorders including the cardiac channelopathies. The processing approach (laboratory technique: immunocytochemistry) for protein distribution visualization has been optimized to be qualitative rather than quantitative. In this sense - each sample will be characterized by "presence" or "absence" of a specific protein at the cell-cell connections. We deem that the qualitative approach is not subject to bias and will ensure accuracy and reproducibility of the results.
 
Secondary outcome measure(s): A potential secondary outcome of the research is whether we can correlate protein distribution in the buccal mucosa with specific genotypes. Our preliminary results on the cohort of patients with ACM suggest that mutations in different genes result in different protein distribution patterns within the buccal mucosa. Being able to predict the gene bearing the disease-causing mutation will significantly reduce the time and cost of genetic sequencing. Identifying the specific gene underlying a heritable arrhythmic disorder is of pivotal importance as increasingly developing genotype/phenotype correlations help individualized risk identification and patient management.
 
Another potential secondary outcome of the research has to do with the effect changes in the patients' treatment plans may have on protein distribution. An example has to do with a protein known as Connexin43 (Cx43). Cx43 is the major gap junction protein expressed in the heart and is responsible for the electrical coupling of the cells and the smooth propagation of electricity throughout the myocardium. Cells at the buccal mucosa also express Cx43. It has been shown that patients with arrhythmic disorders show decreased distribution of Cx43 at the cell borders in their hearts and this "Cx43 remodeling" has been associated with an increased risk for arrhythmias. Our preliminary studies show that patients with ACM, as well as patients with different types of cardiomyopathy (including dilated, hypertrophic and ischemic) show Cx43 remodeling in their buccal mucosa. If a patient shows Cx43 remodeling during initial sampling and in a follow-up visit his clinical care team deems necessary to change his treatment plan (for instance, if he/she is to be started on a different anti-arrhythmic drug) we would like to study Cx43 distribution again during one of his/hers follow up visits. If the new treatment plan results in restoration of Cx43 at the buccal mucosa cell connections, and given how protein distribution in the buccal epithelium mirrors protein distribution in the heart, this finding may be an indication of successful arrhythmia management. It could thus, potentially, provide us with a non-invasive, straightforward and risk-free means to assess therapy efficacy in the future.

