9.3 Definition of the End of Trial

We define the End of the Trial as the day when the last buccal cell sample is obtained and analysed from a volunteer.

Study Procedures

Screening assessments

Participants will fall in either of the following three categories:

1. Patients already diagnosed with a heritable arrhythmic disorder (ACM, hypertrophic cardiomyopathy, dilated cardiomyopathy, Brugada syndrome, Long QT syndrome, catecholaminergic polymorphic ventricular tachycardia). The individuals will only be asked to participate in the study based on their already established diagnosis. No baseline screening assessment will be required.
2. Family members of patients diagnosed with a specific heritable arrhythmic disorder regardless of whether they show disease manifestation or not. These individuals will be asked to participate in the study based on the diagnosis of the proband. No further screening assessment will be required.
3. Family members of SCD victims. If pathology examination of the SCD victims' heart suggests that the individual has died due to a heritable arrhythmic disorder, when his/her family members attend the arrhythmic services at City St George's, University of London for medical evaluation/ risk stratification, they may be asked to participate at the study regardless of whether they show evidence of disease manifestation. No further screening will be required other than the clinical screening that is regularly offered to SCD victim relatives for risk stratification.

Baseline assessments

No baseline assessments are required after the participant has entered the study.

Interventions

The study participants will just be asked to open their mouth. A study team member will rub a soft brush a few times at the inside of their cheek and smear the brush on a microscopy slide. The slide will be sprayed with 70% ethanol to preserve the material and taken to the research laboratory. The patient will have a total of 6 smears taken (3 from each cheek). For the majority of the patients, only a single sampling will be enough which will take place during one of their regular follow-up appointments at the cardiology clinic. There is no pain and no discomfort associated with the procedure and it lasts only a few seconds.

If sampling is being done at-home, the participant will be provided with a kit containing two soft brushes, 6 microscopy slides, a small spray bottle with the fixative, and slide boxes. The

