Regardless of the outcome of the baseline analysis, all participants will be asked to provide the study team members with additional samples up to 3 times/year following their appointment, using a self-sampling kit, and then at their next regular follow-up appointment. If the interim results yielding from the analysis of the self-obtained samples, shows abnormal protein distribution, the medical providers may contact the participant and discuss with them the possibility of bringing their next regular appointment forward for discussion and further evaluation. Regarding the sub-study, the majority of participants will only be asked to provide buccal cells once. In selected cases we may invite them to provide an additional sample at their next regular appointment. Our buccal smear work has shown that one protein in particular, Connexin43, shows restored distribution in response to clinically effective anti-arrhythmic medication. Yet, to date, we do not know what is the mechanism of action through which drugs fix Connexin43 localization and hence restore normal cardiac rhythm. Our sub-study would show whether the drugs act by increasing protein production or merely shifting the protein to junctional sites facilitating electrical conduction.

Methods

Laboratory procedures (if applicable)

The samples obtained will be mailed to [name] research laboratory. The fixed slide will be dipped in blocking buffer (97 ml phosphate buffered saline (PBS), 3 ml normal goat serum, 1 gram of bovine serum albumin and 150 microliters of Triton-X for a total of 100ml). The slides shall be left to incubate for 45 minutes at room temperature. The primary antibody will then be added (I use a liquid-repellent pen to draw a circle around the area where the cells are) diluted in blocking

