Statistical design

Statistical input in trial design

Endpoints

Primary endpoints

The primary end point will be the presence of signal for a specific protein at the junctions of the buccal smear sample. No quantification of immunoreactive signal will be performed as this approach may increase bias. Accordingly, the results for each protein stain will be categorized as “present” or “absent”.

The end point of the sub-study will be whether a protein of interest is expressed at control levels or significantly decreased levels in the presence of a mutation. Accordingly, the results for each protein examined will be categorized as ‘control’ or ‘reduced’.

Secondary endpoints

Not applicable for this study.

Sample size and recruitment

Sample size calculation

The sample size was calculated based on the size of the St. George's and satellite centres' Arrhythmia Services. The number selected constitutes only a fraction of the individuals evaluated and regularly followed at the hospitals involved and will allow us to obtain statistically significant results for each arrhythmic disorder.

Planned recruitment rate

Based on the number of patients/family members evaluated at the arrhythmic services at City St George's, University of London, we estimate that we shall be recruiting approximately 200 individuals per year over the 4 year course of the study.

Statistical analysis plan

Summary of baseline data and flow of patients

The participants will include individuals from 3 groups:

1. Patients already diagnosed with an arrhythmic disorder
2. Relatives of patients diagnosed with arrhythmic disorders to establish risk status
3. Relatives of SCD victims for risk stratification.

There shall be no randomization of the participants and no differential treatment amongst the population. All individuals enrolled will only provide a buccal smear sample.

Primary endpoint analysis

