Both for the primary study (buccal smear immunostaining) and the sub-study (buccal cell western immunoblotting) only frequencies and associations will be assessed. No complex statistical analysis is required for completion of this study. Differences between disease groups in the distribution of immunoreactive signals and levels of protein expression will be assessed in a pairwise fashion with the Fisher exact test. Bonferroni correction will be used to correct P values because of multiple comparisons as appropriate. A p value of less than 0.05 will be considered significant. SPSS 21.0 software shall be used for all analyses. This statistical analysis will be performed by [name]. If expert statistical help is required, the research team will consult medical statisticians within St. George's University of London ([name] [name]) who shall not have access to the participants' personal information.

To describe the precise methods of analysis, I shall use ACM as an example. We have previously shown that in the hearts of patients with ACM a protein known as plakoglobin is dislocated from the cell-cell junctions regardless of the underlying pathogenic mutation or even in cases where no mutation has been identified but the clinical or pathological examination are consistent with a diagnosis of ACM. We used the "presence" or "absence" of plakoglobin from the cell junctions in the buccal mucosa to predict which individuals had ACM in a blinded fashion. Of 39 patient samples obtained, plakoglobin was absent from the cell junctions in 34. It was not, however, absent in samples from patients diagnosed with other forms of cardiomyopathy including hypertrophic, dilated or ischemic cardiomyopathy. This indicated that using plakoglobin distribution in the buccal mucosa as a means to diagnose ACM had sensitivity of 87.1% and specificity of 100%.

Secondary endpoint analysis

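### Sampling schedule contradicts itself and no index sample is named, so repeat samples from one person could enter the primary Fisher tests as independent observations

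*Combined protocol and SAP*

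**What the plan says.** **How many samples**

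- Section 10.4 (Subsequent assessments): whatever the first result, "all participants will be asked to provide the study team members with additional samples up to 3 times/year following their appointment", by self-sampling kit, "and then at their next regular follow-up appointment".
- Section 10.3 (Interventions): "For the majority of the patients, only a single sampling will be enough". Section 6.2 and the project description in the Data Protection Impact Assessment (DPIA, section 25) repeat this. They keep a further sample for selected cases, such as a change of treatment.
- Statistical analysis plan, summary of baseline data and flow of patients: "All individuals enrolled will only provide a buccal smear sample".
- Each smear sampling occasion yields six smears, three per cheek (sections 6.2 and 10.3).

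**What is scored and tested**

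- Synopsis, primary outcome: "each sample will be characterized by" the presence or absence of a given protein at the cell junctions.
- Section 14.2.1: the endpoint is the "presence of signal for a specific protein at the junctions of the buccal smear sample".
- Primary endpoint analysis: disease groups are "assessed in a pairwise fashion with the Fisher exact test", with significance at p below 0.05 and Bonferroni correction where appropriate.

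**What is recorded**

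- The DPIA describes a data collection form that travels with each set of samples. Its listed contents include diagnosis, medication, mutation status, number of slides and who took the sample. They do not include a sampling date or visit number.

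**The concern.** The analysis section rests on a description of sampling that section 10.4 contradicts. If everyone is asked for repeats, the data will hold a varying number of sample sets per person. An endpoint worded per sample does not say how these become one observation per person. Fisher's exact test treats every entry as independent, and repeat smears from one mouth are not.

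Three features make the choice of sample matter:

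- Section 10.4 says that connexin43 distribution is restored by effective anti-arrhythmic medication, so a later sample may measure a different state from the first.
- The same section says that an abnormal self-taken sample may bring the next appointment forward. A further sample is requested at that appointment, so the timing of sampling can depend on the result.
- One form per sample set, with observations logged on spreadsheets, leads naturally to one row per set. Without a date or visit number, the first set may be hard to identify afterwards.

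At stake are the primary p-values and any sensitivity or specificity derived from the same counts.

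**Working it through.** **1. The plan's own figure.** The worked example reports plakoglobin absent in 34 of 39 ACM patient samples: 34/39 = 87.18%, printed as 87.1%. This reads as one result per patient. It comes from the earlier pilot dataset, and no sentence turns it into a rule for this study.

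**2. Occasions per person under section 10.4.** First sample 1 + self-taken samples up to 3 in a year + next appointment 1 = up to 5 in about a year. The DPIA gives appointment intervals of 6 or 12 months. The text does not say whether self-sampling continues after that appointment, so the count stops there.

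**3. Repeats entered as separate observations.** The documents give no within-person correlation (ρ), absence rate or group size. Assumed: ρ = 0.3 to 0.8, 30% absent in both groups (no true difference), 50 people per group, two-sided test at 0.05.

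The design effect is DE = 1 + (m − 1)ρ for m samples per person. A large-sample guide to the resulting type I error is 2[1 − Φ(1.96/√DE)].

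| m | ρ | DE | Guide |
|---|---|---|---|
| 4 | 0.3 | 1.9 | 15.5% |
| 4 | 0.5 | 2.5 | 21.5% |
| 4 | 0.8 | 3.4 | 28.8% |
| 5 | 0.3 | 2.2 | 18.6% |
| 5 | 0.5 | 3.0 | 25.8% |
| 5 | 0.8 | 4.2 | 33.9% |

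Fisher's test is conservative, so simulated rates (beta-binomial data) are somewhat lower:

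- one result per person: about 3%;
- four samples per person: about 13–27%;
- five samples per person: about 17–31%.

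Repeat simulations move these figures by one or two percentage points. Over a wider grid (50 or 100 per group, 10–50% absent), the ranges were about 12–28% for four samples and 14–34% for five, against 1.4–4.4% for one.

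**4. A hypothetical combination rule.** The plan does not propose calling a person abnormal if any sample shows absence. If it were adopted later, a per-sample false-absent rate f would become 1 − (1 − f)^m with independent errors. For an assumed f = 5%:

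- m = 4: 1 − 0.95⁴ = 18.5%;
- m = 5: 1 − 0.95⁵ = 22.6%.

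With ρ = 0.5 the beta-binomial parameters are a = 0.05 and b = 0.95:

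- m = 4: 1 − (0.95/1)(1.95/2)(2.95/3)(3.95/4) = 10.1%;
- m = 5: multiplying the product by a further 4.95/5 gives 11.0%.

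The rate rises as samples accumulate, but less steeply when repeats agree.

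**The case against.** The strongest reply is that the documents point to the person as the unit. The analysis plan's wording is singular. It introduces the ACM example as showing the precise method, and that example predicts which individuals have the disease. The secondary analysis likewise counts 15 of 15 patients. Section 10.4 itself separates the baseline analysis from the additional samples. All of this stands as evidence of intent. It is still not a rule: the singular sentence describes participant flow and conflicts with section 10.4, and the example describes data with no stated repeats.

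Repeats also have a purpose, since one aim is the effect of treatment changes on connexin43. That justifies some of them. However, section 10.4 asks everyone, and no paired analysis is specified.

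A reader might infer more than the documents support:

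- *That the plan will count people several times.* No passage says so; it fails to rule it out.
- *That any absent result will label a person as diseased.* No such rule appears.
- *That sampling intensity differs between disease groups.* Nothing ties visit interval, willingness to self-sample or time enrolled to diagnosis. A difference is possible but not shown.
- *That samples accumulate year after year until 2026.* Section 10.4 can equally be read as ending at the next appointment.

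The schematic in section 6.4 could not be seen and should be checked for a schedule.

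**Conclusion.** The point holds as a contradiction in the sampling schedule combined with a missing index-sample rule. It is not a planned miscount. It goes beyond missing detail because the analysis section relies on a statement about sampling that the procedures section contradicts, and the planned test is valid only with one result per person.

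The consequence would be serious if results were entered per sample: at the assumed values, roughly four to ten times the error rate obtained with one result per person. The exact inflation depends on a correlation, absence rate and group size that the documents do not give. The direction does not, provided repeats within a person are positively correlated.

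**What to change.** 1. **Reconcile the schedule.** Make sections 6.2, 10.3 and 10.4, the analysis plan's participant-flow paragraph and the DPIA description agree on who is asked for repeat samples, how often and for how long.
2. **Name the analysis unit.** In section 14.2.1 and the primary endpoint analysis, state that each participant contributes one present/absent result per protein, taken from the first evaluable sample set after consent. Define evaluable, and state how the smears in a set give one result. Another index sample could be defended; what matters is that one is fixed before results are compared.
3. **Record what the rule needs.** Add sampling date and visit number to the data collection form. For sets already collected, establish whether the order can be recovered from existing records; the documents do not say.
4. **Give later samples their own role.** Use them only for within-person questions: repeatability of the call, and change after a treatment change. Analyse them with a paired method, such as McNemar's test for a before-and-after comparison.

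**Cost:** wording changes, one or two form fields, and possibly some work to date existing sets. No new sampling is needed. The downside is that repeat samples do not add to the primary count.

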If seen at the hospital, the study participants will just be asked to open their mouth. A study team member will rub a soft brush a few times at the inside of their cheek and smear the brush on a microscopy slide. The slide will be sprayed with 70% ethanol to preserve the material and taken to the research laboratory. The patient will have a total of 6 smears taken (3 from each cheek). For the majority of the patients, only a single sampling will be enough which will take place during one of their regular follow-up appointments at the cardiology clinic or using the at-home kit. There is no pain and no discomfort associated with the procedure and it lasts only a few seconds. In selected cases, however, if for instance we want to use the buccal smear to evaluate the effect of a change in medical treatment on protein distribution, the patient might be asked to provide the study team with another sample, again during one of his scheduled regular follow-up visits or using the same self-sampling kit at home. If the at-home kit is being used, the patient will be asked to obtain their own buccal smear samples using the materials provided and mail the slides back to City St George's, University of London.

Exfoliated buccal mucosa cells have been used as a source of material for various genetic tests and in studies of oral cancer but their use in studies of cardiovascular disease has been limited. Previous applications have included analysis of telomere length in buccal cells from patients with ischemic heart failure and measurements of intracellular magnesium levels in patients undergoing radiofrequency catheter ablation for atrial fibrillation. To the best of our knowledge, our study published at *Circulation Arrhythmia and Electrophysiology* 9(2) in 2016, was the first analysis of buccal mucosa cells in patients with a heritable form of heart disease.³ This analysis included 39 patients diagnosed with ACM, a primary myocardial disease characterized by an unusually high burden of arrhythmias and SCD as well as 15 carriers of disease-causing mutations without overt disease manifestation. In a subsequent analysis (unpublished data), 55 additional individuals affected by ACM were sampled and the positive predictive value of our approach in diagnosing the disease was 91.9%. Although highly arrhythmogenic, ACM is a

[figure not shown]

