- Research is not used to make decisions directly affecting individuals
- Short retention limits
- Restricted access controls
- Other (please specify)

Samples will be identified by a study ID number only. No personal data will be noted on the slides.

A key linking the study ID numbers to specific individuals will be kept in protected workstations at respective hospital sites only accessible by the participants' regular medical team.

How long will you need to hold the personal data for after the study has completed?

Not applicable

How will you make sure that you are holding data for the appropriate length of time and no longer?

Not applicable

How will the data be held /stored?

Personal data for all patients/family members are routinely held in medical files and electronically by the individuals' regular medical care providers. There shall not be shared with the principal investigator.

Will you be using any electronic and/or paper Case Report Forms (CRFs) to collect data? If so what are these and how will they be held securely and managed at the end of the project?

A data collection form, not including any personal data, will accompany each set of slides or cell suspension sample. This will include:

- The arrhythmia syndrome the participant has been diagnosed with

- Whether the participant has a family history of sudden cardiac death
- Whether the participant is taking any regular medication
- Whether the participant has been diagnosed with additional medical conditions
- Whether the participant is bearing a known disease-causing mutation
- The number of slides obtained (or if participating in the sub-study whether a single or double round of toothbrush rubbing was required to obtain sufficient cells)
- The team member obtaining the smears/cell sample (or the participant if using the at-home kit)

These will be completed by the participant's regular medical providers.

Following completion of the immunohistochemical/western immunoblotting analysis the principal investigator will complete the second part of the form with any changes observed in the distribution/expression levels of key proteins investigated.

There shall be no personal data noted on the form.

The forms will be held in [name] office at City St George's, University of London. The office is locked and accessible only by the PI.

Upon completion, they shall also be scanned and an electronic copy held in [name] St George's, University of London workstation accessible by the PI only.

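### Who took the smear (clinic staff or the participant at home) is recorded but never used in the analysis, so sampling mode can be confounded with time for Cx43 and may be confounded with disease group

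*Combined protocol and SAP*

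**What the plan says.** The primary endpoint is binary: "the presence of signal for a specific protein at the junctions of the buccal smear sample", scored present or absent (Primary endpoints).

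The smears behind it can be collected in two ways. In clinic, a team member brushes the cheek, makes the smear and sprays it with ethanol (6.2 and 10.3). At home, the participant does all of this by following a video, lets the slide dry and posts it (6.2 and 10.3). The first sample may be of either kind (6.2).

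Section 10.4 then asks all participants for "additional samples up to 3 times/year following their appointment, using a self-sampling kit, and then at their next regular follow-up appointment". A sample prompted by a treatment change is to be taken "again during one of his scheduled regular follow-up visits or using the same self-sampling kit at home" (6.2). No section requires it to match the first sample's mode.

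The data collection form described in the DPIA (section 25) has an entry for "The team member obtaining the smears/cell sample (or the participant if using the at-home kit"). Sampling mode is therefore known for every set of slides.

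The Primary endpoint analysis section states that "No complex statistical analysis is required for completion of this study". It compares disease groups in pairs with the Fisher exact test, with Bonferroni correction where appropriate. It mentions neither the collector nor stratification, and it does not say which of a participant's several samples is analysed. The Secondary endpoint analysis section lists the effect of treatment changes on Cx43 as an aim but names no test for it. The sensitivity-analysis section only refers back to the text above it.

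**The concern.** Disease is read from the absence of signal. If a self-taken smear is thinner or less well fixed and loses signal for that reason, it is scored the same way as disease. Two comparisons are exposed.

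- **Before/after Cx43.** With a clinic baseline and a kit follow-up, extra signal loss in the kit hides restoration or looks like new loss. With a kit baseline and a clinic follow-up, it looks like restoration. The synopsis treats restored Cx43 as a possible sign of successful arrhythmia management, so the error would bear on that interpretation.
- **Disease groups.** If one group uses the kit more than another, extra signal loss in the kit adds to the apparent difference between them.

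The plan records the one variable needed to separate these explanations and then leaves it out.

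**Working it through.** **The plan's own figure.** The target is given as "We anticipate to recruit 800 participants for this study over the course of 4 years", with recruitment of "approximately 200 individuals per year over the 4 year course of the study": 200 × 4 = 800, which agrees. This is recruitment arithmetic, since "The sample size was calculated based on the size of the St. George's and satellite centres' Arrhythmia Services". The documents give no expected rates, power, kit share or error rate by mode. Every error rate, kit share and group size below is an assumption, shown over a range.

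**Before/after, no true change.** Take 50 participants truly 'present' at both times, a clinic baseline read without error, and a kit follow-up with false 'absent' probability *a*. All discordant pairs then go one way. With *k* of them, the two-sided exact McNemar p-value is 2 × 0.5^*k*:

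- *k* = 5: 0.0625, not significant
- *k* = 6: 0.031, significant

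The chance of a spurious significant change is P(X ≥ 6) with X ~ Binomial(50, *a*):

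| *a* | Spurious significant result |
|---|---|
| 5% | 3.8% |
| 10% | 38.4% |
| 20% | 95.2% |

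Reversing the order (kit, then clinic) gives the same probabilities for spurious restoration.

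**Before/after, true restoration of 50%.** With a clinic baseline and a kit follow-up, observed restoration is 0.5 × (1 − *a*): 47.5%, 45% and 40% at *a* = 5%, 10% and 20%.

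**Disease groups, no true difference.** Take 100 per group, with false 'absent' rates of 10% by kit and 2% in clinic. A group with kit share *s* has an expected 'absent' rate of 0.10*s* + 0.02(1 − *s*). The rejection probability of the two-sided 0.05 Fisher test, by enumerating both binomials, is:

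| Kit shares | Expected 'absent' rates | p < 0.05 |
|---|---|---|
| 80% v 20% | 8.4% v 3.6% | 20% |
| 60% v 40% | 6.8% v 5.2% | 4.0% |
| 50% v 50% | 6.0% v 6.0% | 2.4% |

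With 5% by kit and 2% in clinic, the same three rows give 3.9%, 1.7% and 1.4%. None of these figures includes a Bonferroni correction. Inflation needs both a difference between modes and an unequal mix of modes.

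**The case against.** The strongest reply is that no harm has been shown. The documents contain no evidence that self-taken smears read differently. That stands, and it is why the size is conditional. They contain no evidence of agreement either, and the plan includes no check of it.

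A reader might infer more than the text supports in four ways.

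- **That mode is confounded with disease group.** No section ties kit use to diagnosis, to being a relative or to site, and section 10.4 asks all participants for kit samples. Equal mixes produce no inflation.
- **That the group error is very large.** At 10% v 2% and 100 per group, a group sampled wholly by kit against one sampled wholly in clinic gives p < 0.05 in 59% of studies. Nothing suggests such a split, and stratification could not repair it because each stratum would hold only one group. Bonferroni also reduces it: over the 15 pairs of the six disorders listed in 10.1, as an illustration, 59% becomes 21%.
- **That the before/after comparison must mix modes.** The sentence in 10.4 ends with a sample at the next regular appointment, so a clinic-to-clinic pair may exist. A kit baseline is also allowed. What is missing is a rule for choosing the pair.
- **That the Fisher test is planned for the before/after data.** The plan assigns it to differences between disease groups. For Cx43 it names no test, and pooling across modes is inferred from silence.

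Posting does not cleanly separate the modes either. Sections 6.2 and 10.3 say clinic slides are taken to the laboratory, whereas 10.5.1 says without qualification that samples are mailed. The person collecting and fixing the smear still differs. The protein-expression sub-study is sampled on site only and is unaffected.

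**Conclusion.** The concern holds in a limited form. Both modes feed one binary endpoint, mixed-mode pairs are permitted, the collector is recorded, and the analysis does not use it. Sampling mode **can** be confounded with time for Cx43, and **may** be confounded with disease group if kit use turns out unequal.

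The Cx43 comparison is the more exposed because it needs no imbalance between groups. A 10% excess of false 'absent' readings at home is enough for a spurious result in 38% of studies of 50 clinic-then-kit pairs; at 5% the figure is 3.8%. That calculation assumes error-free clinic readings and participants truly 'present' throughout. The synopsis has in mind patients abnormal at first sampling, for whom the direct effects are diluted restoration (clinic then kit) or false restoration (kit then clinic).

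The group comparison is sensitive only to a marked imbalance: 20% at 80/20, but 4.0% at 60/40.

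**What to change.** 1. **Cx43 before/after.** Make same-mode pairs primary: clinic with clinic, using the sample already requested at the next appointment, or kit with kit. Use a paired exact test, and report mixed-mode pairs as secondary.
2. **Disease groups.** Name one analysed sample per participant and tabulate collector by group. Then either stratify by collector (exact conditional or Mantel-Haenszel test) or repeat the comparison in clinic samples only as a sensitivity analysis. State that stratification cannot help where a group has only one mode.
3. **Checking the modes.** Report 'absent' rates by collector within each group. Participants without overt disease are not a sufficient reference on their own, because some may carry mutations and their 'absent' readings may be real.
4. **Text.** Reconcile 6.2 and 10.3 with 10.5.1 on whether clinic slides are taken or mailed to the laboratory.

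Items 1 to 3 are changes to the analysis plan on a variable already collected. The cost is some loss of power and fewer usable pairs if the modes do not in fact differ.
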